#### **7.6 Drug logistics and accountability**

All study medication and study ASA need to be stored at the investigational site according to the labeled storage advice and in accordance with Good Clinical Practice (GCP) and GMP requirements. Study medication and study ASA should not be stored above 30°C. The study medication and study ASA are to be kept in a limited access and secure area that cannot be

accessed by unauthorized personnel. Site personnel will confirm receipt of study medication and study ASA via IxRS and will use study medication and study ASA only for this study and in accordance with this protocol. Receipt, distribution, return, and destruction (if any) of the study medication and study ASA must be properly documented according to local regulation and specified procedures.

Written instructions on medication destruction for unused study medication and study ASA returned to the sites by the patient as well as undispensed study medication and study ASA will be made available to affected parties as applicable.

## 7.7 Treatment compliance

Treatment compliance for the study medication and study ASA will be assessed at each study visits by interview and by counting the tablets returned by the patient to the site and will be documented in the eCRF. Any discrepancies between actual and expected amount of returned study medication and study ASA must be discussed with the patient at the time of the visit, and any explanation must be documented in the eCRF and, if appropriate, in the patient's medical record.

The date of first dose, the last dose, and dose interruptions of either study medication or study ASA will be reported in the eCRF. Patients with temporary interruption of study medication and/or ASA for medical reasons should restart study medication and/or study ASA administration again as soon as medically indicated.

## 8. Non-study therapy

### 8.1 Prior and concomitant therapy - amended

Generally, all prior (within 30 days prior to randomization) and concomitantly taken drugs (as specified in the eCRF) need to be recorded in the eCRF. During the study, concomitant therapy will be recorded at the study visits, or at the time of occurrence of any efficacy outcome events, bleeding events, and SAEs. In addition, any remedial therapy for non-serious-AEs (if AEs are subject to reporting) should be documented.

#### Clopidogrel and other non-study antiplatelet treatment

Patients who enter the study receiving additional antiplatelet therapy will have non-study antiplatelet therapy discontinued when study medication is started.

If deemed required by the investigator, the use of clopidogrel concomitantly with study drugs is allowed at the time of randomization. It is strongly recommended that any course of clopidogrel is kept to the minimum necessary to comply with local standard of care and international practice guidelines (typically 30 days, or up to 60 days for some drug-coated products or devices). Clopidogrel will not be supplied as a study medication.

During the course of the study, for enrolled patients who require use of clopidogrel for a new indication (e.g., indication for PCI with or without stenting), use of clopidogrel is allowed

 Text revised with Protocol Amendment 4 (change no. 17)

 Text in this section was revised with Protocol Amendment 4 (change no. 9) and Protocol Amendment 5 (change no. 3).

(see Section [7.4.4](#)). At the discretion of the investigator, study medication may be used along with clopidogrel or interrupted until the patient no longer requires clopidogrel. The duration of clopidogrel use should follow standard of care and applicable international guidelines.

Treatment with other P2Y12 antagonists, such as prasugrel or ticagrelor may be administered according to usual practice, but the study drug must be interrupted if such drugs are used long-term.

The concomitant use of non-steroid anti-inflammatory drugs (NSAIDs) and non-study antiplatelet therapy during the study (except clopidogrel in the initial study phase) is strongly discouraged since it increases the risk for bleeding. However, if an NSAID drug is indicated, the lowest possible dosage must be selected.

For patients at risk for ulcerative gastrointestinal disease or bleeding or who develop symptoms of these complications during the study, an appropriate gastro-protective prophylactic treatment may be recommended by the investigator, but will not be supplied as study medication.

### **Systemic anticoagulation**

The following drugs are regarded as relevant in terms of influencing coagulation:

- unfractionated heparin and its derivatives (i.e., including low molecular weight heparin (LMWH)),
- vitamin K antagonists,
- novel or Non-VKA oral anticoagulants (NOACs),
- fibrinolytic treatment is allowed during the intervention/surgery, but it must be stopped no later than 24 hours before randomization into the trial.

The use of any of these drugs needs to be recorded in the eCRF.

Patients with a foreseeable need for systemic anticoagulation after the qualifying revascularization procedure should not be enrolled in the study (see Section [6.2](#)). Patients who develop a need for anticoagulant therapy during the study period (e.g., thromboprophylaxis in patients undergoing major orthopedic surgery, acute VTE, atrial fibrillation, mechanical aortic valve replacement, etc.) must interrupt study treatment with rivaroxaban or placebo, while study ASA might be continued at the discretion of the investigator. Study treatment should be restarted in patients who no longer have a need for non-study anticoagulant therapy as soon as possible after the discontinuation of the non-study anticoagulant therapy (e.g., after completion of anticoagulant thromboprophylaxis or anticoagulant treatment for VTE). Bridging or temporary overlap of study medication with anticoagulant therapy may be appropriate, considering the patient's need, risk, and clinical setting. In case of questions, please consult the Study Helpline.

### Prohibited therapy while on study medication

- systemic treatment with strong inhibitors of both CYP3A4 and P-gp inhibitors (e.g., systemic azole antimycotics, such as ketoconazole, and human immunodeficiency virus [HIV]-protease inhibitors, such as ritonavir), or strong inducers of CYP3A4 (e.g., rifampicin, rifabutin, phenobarbital, phenytoin and carbamazepine) at the time of screening or their anticipated use during the study;
- use of antiplatelet therapy other than the protocol specified background antiplatelet therapy of study ASA or clopidogrel is prohibited during the study. This includes drugs with known significant antiplatelet effects such as cilostazol, prasugrel and ticagrelor.
- additional anticoagulant(s) (e.g., warfarin sodium or vitamin K antagonists, heparins, Factor II or Xa inhibitors) concomitantly with study medication are prohibited.
- NSAID (except ASA) may be used concomitantly on a temporary basis, but should be avoided for chronic use (> 4 weeks) during the study;
- any non-study ASA use will not be permitted. For management of CABG and PCI during the study, refer to Section 7.4.3 and Section 7.4.4. Other non-ASA medications should be used for conditions such as pain relief and fever reduction.

These prohibited therapies may be administered on a temporary basis in combination with the study drug if deemed medically appropriate. In general, the investigator should consider temporarily discontinuing study medication if the treatment could result in an increased risk of bleeding (e.g., strong inhibitors of both CYP3A4 and P-gp, or anticoagulants). Study drug medication may be restarted after the prohibited therapy has been discontinued and after completion of a suitable washout period at the investigator's discretion.

Study medication should be temporarily interrupted, if the patient:

- undergoes PCI, CABG, or any other surgical procedure, or medical condition that may require temporary interruption of study drug, or use of prohibited therapy due to bleeding risk or use of open-label anticoagulants,
- experiences a significant bleeding event,
- develops a new neurological deficit or significant alteration in mental status,
- develops a platelet count <50,000/ $\mu$ L,
- has any serious adverse event possibly related to or exacerbated by study drug administration,
- requires a prohibited therapy on a temporary basis.

 Systemic treatment with fluconazole is permitted.

 Bullet point revised with Protocol Amendment 4 (change no. 22a).

 Bullet point revised with Protocol Amendment 4 (change no. 22b and 22c).

 Text revised with Protocol Amendment 4 (change no. 17).

Study medication can be resumed at a time when in the opinion of the investigator it is safe to do so.

### Discontinuation of Study Drug for a Vascular Procedure

**Table 8–1** depicts the approximate equivalent dose of subcutaneous enoxaparin (mg/kg) relative to rivaroxaban 2.5 mg at given time points following its administration, and should be used to assist the investigator in deciding which dose of enoxaparin or equivalent dose of another antithrombotic agent to administer in the event when a patient may have to undergo an emergency interventional coronary procedure or pharmacologic reperfusion while receiving study drug.

**Table 8–1: Comparative antithrombotic effect at given time points following rivaroxaban 2.5 mg administration to subcutaneous enoxaparin doses**

Time after 2.5 mg Rivaroxaban Administration	Equivalent Enoxaparin Dose
3 h	0.15 mg/kg
6 h	0.1 mg/kg
> 9 h	0 mg/kg

Source: [Mega et al. 2012]

When thrombolysis is required within 3 hours of the last study drug administration, it may be necessary to unblind the patient at the discretion of the investigator to estimate the dose of enoxaparin to be administered; in the case the patient is in the rivaroxaban treatment group, the subcutaneous dose of enoxaparin should be adopted as given in **Table 8–1**.

In case of urgent PCI for acute ischemic event, the investigator should discontinue study medication and initiate therapy with non-study ASA prior to PCI with non-enteric coated formulation. The loading dose of non-study ASA may be considered. In addition, consider intravenous administration of 0.5 mg/kg of enoxaparin or its antithrombotic equivalent in patients who undergo PCI. In the event that a patient requires a non-emergency revascularization procedure (PCI or CABG), study medication should be stopped approximately 24 hours before the procedure, if possible, and appropriate anticoagulant or antiplatelet therapy should be instituted as medically indicated (including DAPT).

 Depending on the bleeding risk, the patient may, at the discretion of the managing physician, resume study medication thereafter, but no earlier than approximately 12 hours after the arterial sheath has been removed (for patients undergoing PCI) or after the post-procedural drains have been removed (for patients undergoing CABG surgery), and the last dose of parenteral anticoagulant therapy has been administered.

 Table derived from Attachment 6 of the study protocol of the ATLAS ACS 2 TIMI 51 trial (The second trial of Anti-Xa Therapy to Lower cardiovascular events in Addition to standard therapy in Subjects with Acute Coronary Syndrome), which is online accessible through the website of the New England Journal of Medicine in the supplementary material section (last accessed on 14-FEB-2015):

<[http://www.nejm.org/doi/suppl/10.1056/NEJMoa1112277/suppl\\_file/nejmoa1112277\\_protocol.pdf](http://www.nejm.org/doi/suppl/10.1056/NEJMoa1112277/suppl_file/nejmoa1112277_protocol.pdf)>

 First sentence was removed with Protocol Amendment 4 (change no. 22d).

## **8.2 Post-study therapy**

After discontinuation of study medication (either at study end or in case of permanent premature discontinuation), initiation of standard of care therapy is the responsibility and at the discretion of the investigator.

## **8.3 Background non-antithrombotic therapy**

Given the prevalence of potentially modifiable risk factors and concomitant conditions such as diabetes, hyperlipidemia, hypertension, or smoking in this study population, aggressive treatment and life-style modification are clinically warranted. It is recommended that patients be treated in accordance to standard of care and applicable international/local guidelines.

## **9. Procedures and variables**

### **9.1 Tabular schedule of evaluations - amended**

Please note: As this is an event-driven study, patients participating in this study will have different numbers of study visits.

Patients will be assessed for study participation prior to, or after, the qualifying revascularization whereas this procedure is not considered to be a study visit. On-site study visits for the patients at the investigational site are planned at Screening, Randomization, 1, 3, 6, and 12 months after randomization, and then every 6 months until the end of the study. Upon announcement of study end, patients will come to the clinic for a final on-site EOT visit followed by a telephone contact (post-study treatment follow-up visit) one month later.

The following visit abbreviations are used in the description of the visit schedule:

ScV: Screening visit (to be performed up to 30 days prior to but no later than 10 days after Rev; screening procedures can be performed over multiple days if necessary)

Rev: Day of the qualifying revascularization procedure (not considered a study visit).

RxV: Randomization visit (time point of randomization = [T0]), to be performed as soon as possible but no later than 10 days after Rev once hemostasis is assured.

V1: Visit 1, to be performed 1 month after RxV with an accepted time window of  $\pm$  10 days.

V2-4: Visits 2, 3, and 4; to be performed 3, 6, and 12 months after RxV with an accepted time window of  $\pm$  4 weeks.

V5-Vx: Visit 5 to Visit 5+n (where n is the number of additional treatment phase on-site visits beyond Visit 5) to be performed at regular intervals of 6 months with an accepted time window of  $\pm$  4 weeks; continued until individual premature

 Sentence revised with Protocol Amendment 4 (change no. 17).

 Revised with Protocol Amendment 4 (change no. 3).

 Prior to Protocol Amendment 4, 10 days was 7 days (change no. 2).

permanent termination of the study (not study drug treatment; see Section 6.3) or announcement of study end.

EOT: End of treatment visit, to be performed within 4 weeks after announcement of study end or upon individual termination of the study (not premature study drug discontinuation; see Section 6.3). No further study medication will be dispensed at this visit.

PS-FU: Post-study treatment follow-up visit by phone call, to be performed one month after the EOT visit with an accepted time window of  $\pm$  1 week.

Clinic visits or procedures should be scheduled as close to the specified interval as possible, and preferably within the defined window. If it is not possible for the patient to return within the visit "window", or perform the required study procedures especially due to unforeseen circumstance or technical feasibility beyond the control of the patient or the study center, then the visit or procedure should be scheduled as close to the interval as is convenient for the patient and the study center.

---

 Paragraph revised with Protocol Amendment 4 (change no. 17).

**Table 9–1: Schedule of assessments - amended**

Timelines	ScV a	Qualifying revascularization (Rev)	RxV a (T0)	Treatment Phase						PS-FU 1 Mo post EOT
				V1	V2	V3	V4	V5-Vx	EOT visit b	
				1 Mo	3 Mo	6 Mo	12 Mo	every 6 Mo		
Visit Window (weeks if not otherwise specified)	-30 days before, to +10 days after, Rev 		Up to +10 days after Rev 	±10 days	±4	±4	±4	±4		±1
Type of Visit	Visit		Visit	Visit	Visit	Visit	Visit	Visit	Visit	📞
Informed consent	●									
Demographics	●									
Medical / surgical history	●									
Laboratory tests c	●									
Serum pregnancy test d	●									
Inclusion/Exclusion	●									
Revascularization procedure (surgical or endovascular)		◆								
Documentation of revascularization details			● 							
Randomization (IxRS)			●							
Concomitant medications e	●		●	●	●	●	●	●	●	
1 st study drug			●							
Drug dispense			●	●	●	●	●	●	●	
Drug accountability				●	●	●	●	●	●	
Vital Signs	●		●	●	●	●	●	●	●	
Study efficacy outcomes	●<			continuous reporting						→
Study safety outcomes (bleeding events)	●<			continuous reporting						→
AE/SAE reporting f	●		●	●	●	●	●	●	●	
ABI/TBI h	● g			●	●	●	●	●	●	
Questionnaires (EQ-5D,			●	●	●	●	●	●	●	

(footnotes are provided on the next page)

53 Schedule revised with Protocol Amendment 4 (change no. 2).

54 Schedule revised with Protocol Amendment 4 (change no. 3).

55 Schedule revised with Protocol Amendment 4 (change no. 17).

**Table 9–1: Schedule of assessments - amended**

Timelines	ScV a	Qualifying revascularization (Rev)	RxV a (T0)	Treatment Phase						PS-FU 1 Mo post EOT
				V1	V2	V3	V4	V5-Vx	EOT visit b	
				1 Mo	3 Mo	6 Mo	12 Mo	every 6 Mo		
Visit Window (weeks if not otherwise specified)	-30 days before, to +10 days after, Rev 		Up to +10 days after Rev 	±10 days	±4	±4	±4	±4		±1
WIQ, HCRU) PAD symptom status 										
Vital status										•

 ♦ = non-study procedure (change no. 17); • = study procedure to be performed at specified visits; ☎ = post-study treatment telephone contact

**Abbreviations:** ABI/TBI = Ankle (Toe) - Brachial - Index; AE = adverse event; EOT = end of treatment; EQ-5D = European Quality of Life-5 Dimensions questionnaire; IxRS = Interactive Voice and Web Response System; Mo = month; V = visit; Rx = randomization; SAE = serious adverse event; Sc = Screening; WIQ = Walking Impairment Questionnaire, HCRU= HealthCare Research Utilization (see Section 9.7.3) (change no.17)

- a: Screening visit can be performed at the same time as randomization visit, if all required tests for eligibility criteria are available at that time. Screening period is 30 days before or up to 10 days (change no. 3) after the revascularization procedure. Randomization should be done as soon as possible (but within 10 days [change no. 2]) after the qualifying revascularization procedure.
- b: End of treatment visit is to be performed within 4 weeks after announcement of study end, or once the patient has permanently withdrawn from the study.
- c: Laboratory tests required to verify the eligibility criteria (creatinine/eGFR) are to be collected per the site's standard of care and assessed through a local lab. Creatinine/eGFR must not be older than 30 days prior to the qualifying revascularization (change no. 10). If the patient's eGFR is <30 mL/min/1.73 m^2 prior to the procedure, it must remain to be >15 mL/min/1.73 m^2 72 hours after the procedure in order (change no. 17) to enroll and randomize the patient.
- d: Required in women of childbearing potential only. A pregnancy test must not be older than 7 days prior to randomization.
- e: Planned post-procedural concomitant clopidogrel allowed at the discretion of the investigator, see Section 8.1
- f: Only AE/ SAEs not exempted from adverse event reporting and specified in the protocol need to be documented (see Section 9.6.1.3 (change no.17).
- g: ABI/TBI values used at screening may be historical (captured in the patient's medical history), but must not be older than 12 months prior to the qualifying revascularization procedure (change no. 5). If an ABI/TBI is performed during screening to assess eligibility, it must be completed prior to, or at the time of, the qualifying revascularization (change no. 6).
- h: ABI/TBI assessments performed after informed consent is obtained must be performed per the guidance in the ABI/TBI Site Manual.

56 Schedule revised with Protocol Amendment 4 (change no. 12).

57 Single footnotes of Table 9-1 were revised with Protocol Amendment 4. All changes are included behind the respective text for better readability.

58 Footnote revised with Protocol Amendment 5 (change no. 7).

59 Footnote revised with Protocol Amendment 5 (change no. 7).

60 Footnote added with Protocol Amendment 5 (change no 5).

## 9.2 Visit description

### 9.2.1 Timing of assessments

#### 9.2.1.1 Screening Visit (ScV): 30 days before, or up to 10 days after qualifying revascularization procedure - amended

The ScV is required to assess the eligibility of the patient. After obtaining signed informed consent, the investigator will review or perform all medical evaluations required to verify the patient's eligibility for study participation as defined in the inclusion and exclusion criteria. Adverse events reporting begins once the informed consent has been signed.

Demographic data and medical history (including PAD risk factors and vascular disease history) will be recorded at Screening. Laboratory tests should be performed according to the site specific standards, but must, at minimum, include creatinine and eGFR, and a serum pregnancy test in women of childbearing potential. Results of laboratory measurements (ideally obtained during the hospital admission for the qualifying revascularization) should not be older than 30 days prior to the qualifying revascularization; otherwise, tests would need to be repeated. If the site's local laboratory report does not provide eGFR, this value should be calculated (e.g. using the Modification of Diet in Renal Disease [MDRD] formula). All laboratory tests will be performed locally as no central laboratory is involved in this study.

The following measures/documentations will be performed at the screening visit:

- obtaining informed consent;
- documentation of demographic characteristics (for details see Section 9.3.1);
- documentation of medical history (for details see Section 9.3.2) and surgical history;
- review laboratory test data for the patient, if creatinine/eGFR assessments were performed more than 30 days prior to the qualifying revascularization, they must be redrawn and if serum pregnancy test (females with childbearing potential only)was performed more than 7 days ago prior to the qualifying revascularization a repeat pregnancy test must be performed;
- evaluate for all inclusion- and exclusion criteria;
- documentation of prior (within the last 30 days prior to randomization) and concomitant medication. Chronic treatment with prescription antiplatelet therapies (except already ongoing treatment with low-dose ASA that can be continued as study ASA 100 mg od) should be stopped at the time of randomization;
- assess vital signs (blood pressure, pulse rate);
- check for the occurrence of AEs/SAEs since the signing of the ICF (only AEs/SAEs not exempted from AE/SAE reporting need to be reported; for details see Section 9.6.1.3);

 First two paragraphs revised with Protocol Amendment 4 (changes no. 3 and 10).

 Sentence revised with Protocol Amendment 4 (change no. 17).

 Sentence revised with Protocol Amendment 4 (changes no. 10 and 17).

- perform ABI (or TBI) if no ABI/TBI data are available for the patient within the last 12 months prior to the qualifying revascularization; ABI/TBI assessments performed after informed consent is obtained must be performed per the guidance in the ABI/TBI Site Manual.

If the patient is eligible for study participation, the site investigator should make all organizational arrangements required for prompt randomization of the patient to study treatment as soon as feasible, but no more than 10^66 days after the qualifying revascularization procedure (for treatments to be administered, see Section 7.1).

### 9.2.1.2 Randomization visit (RxV): 0-10 days after the qualifying revascularization procedure - amended

 After meeting all inclusion criteria and none of the exclusion criteria, eligible patients will be randomized by accessing the IxRS system and receive study medication and study ASA as soon as feasible, but no more than 10 days after the qualifying revascularization procedure. The first dose of study medication should be given immediately, but no more than 24 hours after randomization, if study drug can be safely administered (see Section 7.4). Planned additional treatment with clopidogrel after the qualifying revascularization procedure is allowed at the discretion of the investigator, as described in section 8.1.

The following measures/documentations will be performed at the randomization visit:

- randomization of patient (must be performed prior to all other randomization study visit procedures);
- documentation of the details about the qualifying revascularization and its success;
- If laboratory evaluations have been performed and are available per standard or usual care of the subjects in the recent past that reflect baseline hematologic, glucose metabolic, liver, and renal functions, record the relevant and available indices in the eCRF (HbA1c, total cholesterol, HDL cholesterol, LDL cholesterol, ALT(SGPT), AST(SGOT), total bilirubin, hemoglobin, hematocrit, platelet count). The serum creatinine value used to assess eligibility and corresponding eGFR should also be entered;
- dispensing of study medication and study ASA with patient instruction;
- administration of first study medication treatment dose (on-site);
- documentation of any changes in concomitant medication since the last study visit;
- assess vital signs (blood pressure, pulse rate);

 Timepoint for ABI (TBI) changed with Protocol Amendment 4 (changes no. 5 and 10).

 This bullet point was modified with Protocol Amendment 5 (change no. 5).

 Sentence revised with Protocol Amendment 4 (change no. 3).

 Section revised with Protocol Amendment 4 (changes no. 2 and 17)

 Last two sentences revised with Protocol Amendment 4 (change no. 17).

 Sentence revised with Protocol Amendment 4 (change no. 17).

 Sentence revised with Protocol Amendment 4 (change no. 17).

 Bullet added with protocol Amendment 4 (change no. 19)

- check for the occurrence of study efficacy outcome events since the last study visit (these pre-randomization events should be documented on the outcome pages and forwarded by expedited means to the Sponsor's PV; see Section 9.6.1.3);
- check for the occurrence of study safety outcome events (bleeding events) since the last study visit (these pre-randomization events should be documented on the outcome pages and forwarded by expedited means to the Sponsor's PV; see Section 9.6.1.3);
- check for the occurrence of AEs/SAEs since the last study visit; for events exempted from AE/SAE reporting, see Section 9.6.1.3);
- assess the patient's PAD Symptom Status.  
(This assessment, as well as the QoL assessment and Walking Impairment Questionnaire, should reflect the time period prior to the qualifying revascularization procedure);
- QoL assessment with EQ-5D;
- Walking Impairment Questionnaire;
- remind patient to return with the study medication and study ASA dispensed bottles at their next visit.

**Note: Screening and randomization visits can be combined into one single visit, provided that all required information for the patient eligibility assessment are available at that time (e.g., eGFR values).** Study endpoint evaluations and safety evaluations will start from time of signing the ICF. The patient will be instructed to report any hospitalization or other significant illness to the investigator on an ongoing basis during the entire course of the study in order to allow a timely reporting of study efficacy outcome events, bleeding events, and other AEs/SAEs.

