10. Hypersensitivity or any other contraindication listed in the local labeling for ASA or rivaroxaban;
11. Systemic treatment with strong inhibitors of both Cytochrome P450 isoenzyme 3A4 (CYP3A4) and p-glycoprotein (P-gp) inhibitors (e.g., systemic azole antimycotics, such as ketoconazole [fluconazole is permitted], and human immunodeficiency virus [HIV]-protease inhibitors, such as ritonavir), or strong inducers of CYP3A4 (e.g., rifampicin, rifabutin, phenobarbital, phenytoin and carbamazepine) anticipated after randomization or during the study. 

- Exclusion criteria related to bleeding risks or systemic conditions:

12. Medical history or active clinically significant bleeding, lesions, or conditions within the last 6 months prior to randomization, considered to be a significant risk for major bleeding (this may include current medically confirmed gastrointestinal ulceration, presence of malignant neoplasms at high risk of bleeding, current or recent brain or spinal injury, known esophageal varices, vascular aneurysms of the large arteries or major intraspinal or intracerebral vascular abnormalities);
13. Any known hepatic disease associated with coagulopathy or bleeding risk;
14. Any condition requiring dialysis or renal replacement therapy, or a renal impairment at screening assessed with an estimated glomerular filtration rate  $<15 \text{ mL/min}/1.73 \text{ m}^2$ \*  
(\*if a patient's eGFR is  $<30 \text{ mL/min}/1.73 \text{ m}^2$  prior to the procedure, it must remain to be  $>15 \text{ mL/min}/1.73 \text{ m}^2$  72 hours after the procedure to enroll and randomize the patient);  

15. Confirmed acute coronary syndrome (ACS) within 30 days prior to randomization;
16. Major trauma or accidents within 30 days prior to randomization;
17. Any medically documented history of intracranial hemorrhage, stroke, or transient ischemic attack (TIA);
18. Known active malignancy (as determined through review of medical history), excluding local skin cancer (basal or squamous cell carcinoma);
19. Poorly controlled diabetes (at the discretion of the investigator);
20. Severe uncontrolled hypertension (at the discretion of investigator);
21. Overall life expectancy  $< 1$  year.

- Other exclusion criteria:

Exclusion criteria modified via Protocol Amendment 5 (change no. 7).

Exclusion criterion 12 revised with Protocol Amendment 4 (change no. 17).

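### For patients screened before the procedure, no scheduled eligibility check precedes the IxRS call, and the check for interval events is ordered after randomisation

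*Protocol*

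**What the plan says.** Protocol section 9.2.1.2 (randomisation visit) opens with the intended rule: "After meeting all inclusion criteria and none of the exclusion criteria, eligible patients will be randomized by accessing the IxRS system". Its list of visit procedures then begins with "randomization of patient (must be performed prior to all other randomization study visit procedures".

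The items that follow include "documentation of the details about the qualifying revascularization and its success", an update of concomitant medication, and "check for the occurrence of study efficacy outcome events since the last study visit (these pre-randomization events should be documented on the outcome pages". Bleeding events have a matching item, and adverse events are checked too.

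The instruction to "evaluate for all inclusion- and exclusion criteria" appears in section 9.2.1.1, the screening visit. In Table 9-1 the Inclusion/Exclusion row has a single mark, at screening. Screening may take place from 30 days before to 10 days after the procedure, and randomisation up to 10 days after it.

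Several exclusions in section 6.2 are counted back from randomisation or can arise at any time before it. Examples are "Confirmed acute coronary syndrome (ACS) within 30 days prior to randomization" (criterion 15), clinically significant bleeding within 6 months (12), major trauma within 30 days (16) and any history of stroke or TIA (17).

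**The concern.** Amendment 4 opened screening to the 30 days before the procedure. A patient screened then still has the procedure and the peri-procedural period ahead. A stroke, an acute coronary syndrome or a significant bleed in that interval makes the patient ineligible. The one visit item that asks about such events is placed, by an explicit ordering rule, after allocation.

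Once randomised, the patient belongs to the ITT set, which comprises all randomised patients (protocol section 10.2; SAP section 5.1.1), and cannot be replaced (protocol section 6.3.2). The first dose is to follow immediately if it can be given safely, and at the latest within 24 hours. No item requires the event check to come before that dose. At stake are avoidable randomisation of ineligible patients and their possible exposure to study drug. A smaller issue is that the strata used in the primary analysis are the IxRS entries (SAP section 6.2.5), and these are made before the visit documents the procedure or the current medication.

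**Working it through.** **1. When each item is required and when it is scheduled, for a patient screened before the procedure**

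| Item | Required before randomisation? | Scheduled step after the procedure and before the IxRS call? |
|---|---|---|
| Technical success | Yes: inclusion 3, section 9.3.3 | None; documentation is listed after randomisation |
| Patency | Yes: section 9.3.3 | None |
| Clopidogrel status | Yes: section 7.3 ties the stratum to actual use at randomisation | None; the medication update comes after |
| eGFR after the procedure, if below 30 beforehand | Yes: exclusion 14, section 7.4.7, Table 9-1 note c | Stated as a condition of randomising; laboratory tests are marked only at screening |
| New bleeding, ACS, trauma, stroke or TIA | Yes, through exclusions 12, 15, 16 and 17 | None; the event checks are ordered after randomisation |

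For the first four rows the requirement is clear and only a scheduled confirmation is missing. In the last row the check itself comes late.

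**2. Length of the gap.** 30 days before plus 10 days after the procedure gives at most 40 days. From the procedure onward it is at most 10 days.

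**3. Illustration of interval events.** Inputs are N = 6,500 and a control rate of 7.5% per year (protocol section 10.4), read here as a constant hazard. The share *s* of patients with the gap is not in the documents and is my assumption.

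Events = 6,500 × *s* × 0.075 × gap / 365.25

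- 10 days, *s* = 1: 0.075 × 10/365.25 = 0.21%; × 6,500 = 13.3
- 40 days, *s* = 1: 0.075 × 40/365.25 = 0.82%; × 6,500 = 53.4

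| Share *s* | 10-day gap | 40-day gap |
|---|---|---|
| 25% | 3.3 | 13.3 |
| 50% | 6.7 | 26.7 |
| 100% | 13.3 | 53.4 |

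These count primary-type events, not ineligible patients. CV death rules out randomisation. Major amputation is not itself an exclusion. Exclusion 4 covers ALI only before the procedure; later ALI would matter through the patency requirement. In the other direction, bleeding is not in the composite, and section 10.4 expects early event rates above those of its reference trial.

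**4. Effect on power.** First the plan's own figure. I used a log-rank calculation with HR 0.80, one-sided alpha 0.025, the stated discontinuation rates (patients who stop rivaroxaban move to the control hazard), 1.5% per year loss, 15/30/55% accrual over 18 months and 24 further months of follow-up. At each time step, D is the number of events, φ the ratio of patients at risk and θ the current hazard ratio:

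E = Σ D[φθ/(1+φθ) − φ/(1+φ)] / √(Σ Dφ/(1+φ)²)

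Power = Φ(|E| − 1.96), with |E| rescaled to 1,015 events.

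This needs 1,018 events for 90% power, against 1,015 in the plan, and gives 89.9% at 1,015. The plan's figure is reproduced.

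Next, suppose a share of the rivaroxaban arm has no treatment effect (my assumption). Power at 1,015 events is:

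| Share with no effect | Power |
|---|---|
| 0% | 89.9% |
| 1% | 89.3% |
| 2% | 88.6% |
| 5% | 86.5% |

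The extreme case in step 3 is 0.82% of patients, so even on that basis the loss is below 0.6 percentage points.

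**5. Endpoint counting.** The ITT data scope starts at the randomisation date (SAP section 4.5.2). Events before it are not counted as endpoints, whenever they are discovered.

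**The case against.** The opening sentence of section 9.2.1.2 already forbids randomising an ineligible patient. Screening need not close early: "screening procedures can be performed over multiple days if necessary" (section 9.1), and "Screening and randomization visits can be combined into one single visit, provided that all required information for the patient eligibility assessment are available". Inclusion 3 cannot be judged before the procedure, so a complete screening evaluation must extend beyond it. The protocol also expects events after consent to stop some patients. Events are collected continuously from consent, patients are asked to report hospitalisations, and sections 6.3.1, 9.6.1.3.2 and 11.1 provide for screening failures. Only randomisation has a fixed place in the list, so a site may check events before dosing, and the first dose depends on its being safe. The IxRS manual, which is not available here, may require confirmation of eligibility at the call. Allocation is blinded, so affected patients should be balanced between arms. Eligibility deviations are tabulated (SAP section 6.1.4), and analyses by actual procedure and clopidogrel use are planned (SAP sections 6.2.9 and 6.2.10).

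Most of this stands. It rules out a stronger reading that a reader might infer from the ordering rule, namely that success, patency, clopidogrel use and the post-procedure eGFR are first checked after allocation. Other sections require all four beforehand. The gap also largely closes when screening follows the procedure or is combined with randomisation.

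The objection does not remove the remaining conflict. The opening sentence sets a condition, but no scheduled step verifies it for a patient screened early, and the ordering rule places the relevant event checks after the call. Multi-day or combined screening is optional, while screening before the procedure is expressly allowed.

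**Conclusion.** The point holds for patients screened before the procedure. The precondition and the ordering rule in section 9.2.1.2 conflict, and no scheduled step just before the IxRS call confirms the absence of a new excluding event or re-confirms success, patency and clopidogrel use. The consequence is avoidable randomisation, and possible dosing, of ineligible patients who then remain in the ITT set.

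The size is unknown, because the documents give neither the share screened early nor a rate of ineligible randomised patients. The figures of 13 and 53 assume that all 6,500 patients have the 10-day or 40-day gap and a constant 7.5% yearly hazard. A reader might take 53 as a floor, but it is not one: it uses the longest possible gap for everyone and includes events that prevent randomisation in any case or are not exclusions. Nor does the text support a claim that endpoint events are miscounted or that power is materially reduced. The case for change rests on eligibility and safety.

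**What to change.** In section 9.2.1.2, place two steps before the IxRS call:

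- the checks for efficacy, bleeding and adverse events since the last visit;
- a re-confirmation of all inclusion and exclusion criteria, including technical success, patency and the clopidogrel status that defines the stratum.

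Limit the rule that randomisation comes first to procedures that do not bear on eligibility. Add an Inclusion/Exclusion mark at the randomisation visit in Table 9-1. Apply the same order when screening and randomisation are one visit.

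The cost is a few lines of protocol text and one table mark. The event checks, procedure details and medication update are already collected at this visit. Sites do slightly more work before the call, and a few patients become screening failures instead of randomised eligibility deviations.
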